8.3 Investigator Assessment of Adverse Events

8.3.1 Determination of Adverse Event

Oseltamivir was first licensed in 1999, and is currently licensed in most countries (including all countries participating in this study). Cumulative safety and tolerability data for oseltamivir from over 4000 subjects in randomized controlled trials, as well as significant postmarketing surveillance for significant side effects has been published. [28] The most common side effects of oseltamivir include nausea with or without vomiting and headache. It is unlikely that this study will significantly contribute to what is known about oseltamivir safety and tolerability.

Symptoms associated with influenza include: fever, headache, eye irritation, nasal congestion or discharge, sneezing, sore throat, cough, abdominal pain, diarrhea, dyspepsia, nausea, vomiting, chills, fatigue, arthralgia, myalgia, neck pain, malaise, ear congestion or discomfort. Physical findings include the patient appearing flushed, oropharyngeal hyperemia, cervical lymphadenopathy, wheezing, and tachypnea. Recording influenza symptoms as adverse events is neither an appropriate way to capture this data nor is this study likely to significantly contribute to what is known about the signs and symptoms of influenza.

Symptoms captured on the diary cards either in the structured assessment and/or as free text should be assessed to determine if it fits with known presentations of influenza or known side effects of oseltamivir.

Therefore, this study will not capture in the source nor eCRF grade 1-3 adverse events that are known side effects of oseltamivir (as defined in the package insert) nor known signs and symptoms associated with influenza (as noted, or similar to what is noted above).

However, the following still need to be recorded in the source records and the eCRF:

- Adverse events that do not follow side effects of oseltamivir or known signs and symptoms associated with influenza (e.g. visual changes)
- Complications of influenza (e.g. pneumonia, sinusitis, or myocarditis)

- Any adverse events that are judged by the site investigator to be clinically significant (e.g. new onset seizures, acute allergic reactions)
- All Grade 4 (life-threatening) or Grade 5 (death) AEs regardless of association with influenza or oseltamivir
- Serious Adverse Event (SAE) as defined in section 8.2
- Unanticipated Problem that is not an Adverse Event as defined in section 8.2

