7.3.1.2 Symptoms

The symptoms assessed will be those assessed in previous licensure studies with oseltamivir (denoted by the ¶ symbol), [19, 20], as well as the addition of rhinorrhea and symptoms that are frequently a component of influenza (denoted by the § symbol). Using a 4-point scale (0 = absent, 1 = mild, 2 = moderate, 3 = severe), each symptom will be assessed for severity. Subjects will be asked to assess their symptoms twice daily for Study Days 0-7, and once daily for Study Days 8-14.

The symptoms assessed are:

- Cough ¶
- Nasal obstruction ¶
- Sore throat ¶
- Fatigue ¶
- Headache ¶
- Myalgia ¶
- Feverishness ¶
- Rhinorrhea §
- Nausea §
- Vomiting §
- Diarrhea §

Symptoms present at the time of enrollment and not worsened during treatment will not be considered AEs. Any new or worsened symptoms during treatment should be assessed for AEs in accordance with section 8.3.1.

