#### 4.7.2 Adverse Events (Enrolled population, and ITT)

- a. Enrolled Population: Number (%) of subjects with an AE (as defined above) by MedDRA System Organ Class (SOC) and Preferred Term (PT); number (%) of subjects with all AEs irrespective of time since randomization (i.e. including any reported before randomization or after Day 28).
  - Table repeated to show total number of AEs (i.e. allowing a subject to be represented more than once per row, SOC header, and in total numbers).
- b. ITT Population: Number (%) of subjects with an AE (as defined above) by MedDRA System Organ Class (SOC) and Preferred Term (PT); number (%) of subjects with all AEs from Day 0 to Day 28.
  - Table repeated to show total number of AEs (i.e. allowing a subject to be represented more than once per row, SOC header, and in total numbers).
- c. ITT Population: Number (%) of subjects with an AE (as defined above) by MedDRA System Organ Class (SOC) and Preferred Term (PT); number (%) of subjects with all related AEs (definitely related, probably related, possibly related) from Day 0 to Day 28.
  - Table repeated to show total number of AEs (i.e. allowing a subject to be represented more than once per row, SOC header, and in total numbers).
- d. Enrolled Population: List of AEs: Randomized arm, days from randomization to first AE experienced by a subject, subject ID, site, confirmed influenza infection status, days from randomization to AE, days from last dose of study treatment, AE (MedDRA SOC and PT, and verbatim description), severity grade, relatedness to study intervention, outcome, e.g., died/resolved/ongoing, sorted by randomized arm, days from randomization to first AE, subject ID, and, if a subject has multiple AEs, days from randomization to AE.

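### The SAP 4.7.2 adverse-event tables will largely omit ordinary nausea, vomiting, diarrhea and headache and so will understate any tolerability difference; a by-arm diary table would fill the gap

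*Protocol*

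**What the plan says.** **What is not recorded.** Protocol 8.3.1 says "this study will not capture in the source nor eCRF grade 1-3 adverse events that are known side effects of oseltamivir", with known side effects defined by the package insert. The same sentence goes on: "nor known signs and symptoms associated with influenza (as noted, or similar to what is noted above". The section also says "The most common side effects of oseltamivir include nausea with or without vomiting and headache". Its list of influenza symptoms includes headache, nausea, vomiting and diarrhea.

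**What is still recorded.** The same section keeps "Adverse events that do not follow side effects of oseltamivir or known signs and symptoms associated with influenza (e.g. visual changes"), "Any adverse events that are judged by the site investigator to be clinically significant", and "All Grade 4 (life-threatening) or Grade 5 (death) AEs regardless of association with influenza or oseltamivir". It also keeps complications of influenza and serious adverse events.

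**The diary.** Protocol 7.3.1.2 has subjects score each of 11 symptoms from 0 to 3, twice daily on Days 0-7 and once daily on Days 8-14. Nausea, vomiting, diarrhea and headache are among them. Protocol 7.3.1 says that influenza symptoms on the diary are not captured as AEs, and 7.3.1.2 says "Any new or worsened symptoms during treatment should be assessed for AEs in accordance with section 8.3.1".

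**The tables.** SAP 4.7.2 tabulates AEs by MedDRA class and term. For the ITT population it adds the "number (%) of subjects with all related AEs (definitely related, probably related, possibly related) from Day 0 to Day 28". SAP Section 4 makes tables by arm by default.

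**The concern.** The events that the drug is most expected to cause are the ones that the AE data mostly leave out. The related-AE table is the most exposed. Under Protocol 8.3.5, fitting the drug's recognised response pattern counts toward a rating of possible or probable and is required for definite. At grades 1-3, events with that pattern are the ones that 8.3.1 excludes. The referral of new or worsened symptoms back to 8.3.1 leads to the same exclusion.

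With no analysis of these symptoms elsewhere, a small or absent difference in the AE tables could be read as evidence of similar tolerability, when it partly reflects the recording rule. The primary endpoint is not affected.

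**Working it through.** **1. The protocol's own figures.** Protocol Table 1 (prophylaxis studies, oseltamivir 75 mg/day) gives counts out of 1434 on placebo and 1480 on oseltamivir. Rate = count / n. Expected subjects = 280 × rate, since 560 randomized 1:1 gives 280 per arm.

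| Event | Placebo | Oseltamivir | Difference (points) | Expected per 280 |
|---|---|---|---|---|
| Nausea | 62/1434 = 4.32% | 118/1480 = 7.97% | 3.65 | 12.1 vs 22.3 |
| Vomiting | 15/1434 = 1.05% | 31/1480 = 2.09% | 1.05 | 2.9 vs 5.9 |
| Diarrhea | 38/1434 = 2.65% | 48/1480 = 3.24% | 0.59 | 7.4 vs 9.1 |
| Headache | 251/1434 = 17.50% | 298/1480 = 20.14% | 2.63 | 49.0 vs 56.4 |

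These agree with the printed percentages to rounding. Protocol 1.3.2 also reports 10-15% gastrointestinal side effects on oseltamivir in the adult treatment trials. That is 280 × 0.10 = 28 to 280 × 0.15 = 42 subjects in the active arm, but no placebo rate is given beside it.

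**2. What the recording rule does.** Let c be the share of nausea cases that reach the AE form through an exception, taken as equal in both arms. The tabulated difference is then c × 3.65 points. The documents give no value for c, so the values below are assumptions.

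| c | Expected subjects, placebo vs oseltamivir | Difference (points) |
|---|---|---|
| 0% | 0 vs 0 | 0 |
| 5% | 0.6 vs 1.1 | 0.18 |
| 10% | 1.2 vs 2.2 | 0.36 |
| 25% | 3.0 vs 5.6 | 0.91 |
| 50% | 6.1 vs 11.2 | 1.82 |
| 100% | 12.1 vs 22.3 | 3.65 |

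The difference is zero only if nothing passes the exceptions. With equal c the ratio of rates stays at 7.97 / 4.32 = 1.84, but at low c it rests on one or two subjects per arm.

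**3. Whether another planned output shows these effects.**

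- SAP 4.3.3 item j tabulates each symptom separately, but only at Day 0, before treatment.
- SAP 4.9 item a uses one composite: the time until all symptoms score 0 or 1. Drug-related nausea scored 2 or 3 could delay it and nausea scored 1 would not. In either case the effect is mixed with recovery from every other symptom.
- SAP 4.5 reports full and partial courses with reasons. This shows intolerance only when it interrupts treatment.

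None of these isolates nausea, vomiting, diarrhea or headache by arm after baseline.

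**4. A conflict within the protocol.** Section 8.3.1 restricts what is recorded. Section 8.4.1 opens by limiting itself to the AEs to be recorded for the study, but later requires the investigator to document every AE that is directly observed or spontaneously reported. Sites could reasonably follow either text, so c may also vary between sites.

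**The case against.** The rule is deliberate and openly justified. The drug is licensed, much safety data exists, and the protocol expects to add little to it. Safety is not among the listed objectives. This stands as a reason not to record the events. It does not justify by-arm tables that leave the consequence unexplained.

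A reader might go further and infer that the AE tables must show no tolerability difference by construction. The documents do not support that. Clinically significant events of any grade, Grade 4/5 events, serious events and events outside both known profiles are recorded, and each can differ by arm.

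A reader might also infer that the SAP tables ignore the restriction. SAP 4.7.2 refers to an AE definition given earlier. None appears in the SAP text available here, but the introduction and key updates named in its contents were not part of that text, so its absence cannot be asserted.

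Nor is the exclusion left to each investigator's idea of a known effect. Side effects are tied to the package insert and influenza symptoms are listed, with some latitude for similar symptoms. The explicit discretion lies in what is clinically significant, and it adds events to the record.

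Finally, tolerability is not wholly unobserved, because treatment completion and the symptom composite are reported by arm. What is missing is symptom-specific reporting.

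**Conclusion.** The concern holds as a gap in analysis and reporting. Followed as written, the AE and related-AE tables will largely omit ordinary nausea, vomiting, diarrhea and headache, and so will understate any difference between arms. On the illustrative nausea rates, a difference of 3.65 points would appear as about 0.2 to 0.9 points if 5% to 25% of cases were captured.

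This rests on three assumptions: the capture share itself, equal capture in both arms, and rates from prophylaxis at 75 mg/day, whereas subjects here are ill and take 75 mg twice daily. The figures therefore show scale only. No AE hypothesis test is planned, so power is not the issue. It would also be too strong to infer that harm cannot be assessed from this trial, since the diary already holds most of the missing information.

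**What to change.** 1. Add to SAP 4.7 a by-arm ITT table of subjects with new or worsened nausea, vomiting, diarrhea and headache on the diary, relative to Day 0, over Days 0-7. Show each symptom by worst diary grade, with the difference between arms and its 95% confidence interval. Days 0-7 span the 5-day course at the twice-daily diary frequency.
2. Footnote each AE table in SAP 4.7.2 with the exclusion in Protocol 8.3.1 and its exceptions, and make sure that the SAP states the AE definition to which it refers.
3. Reconcile Protocol 8.3.1 with 8.4.1 on which AEs are documented.

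The first two cost one table and a footnote and need no new data. The third is a text clarification. The downside of the diary table is that illness and drug effects are mixed in these symptoms. The blinded, randomized comparison handles this by estimating the net difference between arms, and the table should be described in those terms.

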8.3.2 Period of Assessment

AEs that should be recorded (as defined above) occurring from the time the informed consent is signed through Day 28 will be documented, recorded, and reported. Additionally, after Day 28 AE/SAE related to the pregnancy or the developing fetus will be reported. After the end of the protocol-defined SAE reporting period, sites must report to the safety office serious, unexpected, clinically suspected adverse drug reactions if the study site staff becomes aware of the event on a passive basis.

8.3.3 Assessment of Adverse Event

The Investigator will evaluate recorded AEs with respect to **Seriousness** (criteria listed above), **Severity** (grading), and **Causality** (relationship to study agent and relationship to research) according to the following guidelines.

8.3.4 Severity

The Investigator will grade the severity of recorded AEs according to the “Division of AIDS Table for Grading the Severity of Adult and Pediatric Adverse Events” Version 1.0, December, 2004: (Clarification August 2009) which can be found at:

http://rsc.tech-res.com/Document/safetyandpharmacovigilance/Table_for_Grading_Severity_of_Adult_Pediatric_Adverse_Events.pdf

8.3.5 Causality of Adverse Event to the Intervention

The Investigator will assess recorded AEs for causality. A causal relationship means that the study intervention/procedure caused (or is reasonably likely to have caused) the AE. This usually implies a relationship in time between the intervention and the AE (e.g. the AE occurred shortly after the subject received the study intervention/procedure).

The clinician who examines and evaluates the subject will determine the event’s causality. Acceptance that an AE is causally related to the intervention usually requires a plausible mechanism of action (i.e., a believable sequence of events by which the intervention brought about the AE).

The best estimate of the Investigator at the time of reporting of the causal relationship between the experimental intervention and an adverse event and the degree of certainty about causality will be graded as follows:

Unrelated

Adverse event is clearly due to extraneous causes (e.g., underlying disease, environment). For an “unrelated” designation of causality, there should be a clear and plausible cause that excludes the possibility that the adverse event could be caused by the study treatments.

Unlikely (must have 2)

Adverse event:

1. does not have temporal relationship to intervention
2. could readily have been produced by the subject’s clinical state
3. could have been due to environmental or other interventions
4. does not follow known pattern of response to intervention
5. does not reappear or worsen with reintroduction of intervention

Possible (must have 2)

Adverse event:

1. has a reasonable temporal relationship to intervention
2. could not readily have been produced by the subject’s clinical state
3. could not readily have been due to environmental or other interventions
4. follows a known pattern of response to intervention

Probable (must have 3)

Adverse event:

1. has a reasonable temporal relationship to intervention
2. could not readily have been produced by the subject’s clinical state or have been due to environmental or other interventions
3. follows a known pattern of response to intervention
4. disappears or decreases with reduction in dose or cessation of intervention

Definite (must have all 4)

Adverse event:

1. has a reasonable temporal relationship to intervention
2. could not readily have been produced by the subject’s clinical state or have been due to environmental or other interventions
3. follows a known pattern of response to intervention
4. disappears or decreases with reduction in dose or cessation of intervention and recurs with re-exposure

8.4 Investigator Reporting Responsibilities to the Sponsor

8.4.1 Adverse Events

AEs that are to be recorded for this study (as noted above) will be fully and completely documented on the AE eCRF and in the subject’s clinical chart.

In the event that the subject is withdrawn from the study due to an AE, it must be recorded on the eCRF as such. The subject should be followed and treated by the Investigator until the adverse event has resolved or stabilized, even if this extends past the 28 day follow up period. It is up to the clinician to determine that the AE/SAE is resolved or has reached a stable state, after which no further follow-up is necessary. There should be documentation to support that determination.

Once an AE or SAE is known, research team members at the study site should ensure that subjects receive appropriate care. All actions taken by the Investigator after observing an AE or SAE should be documented, including increased monitoring of the subject, suspension of the treatment, etc.

Assessment of safety will include clinical observations and monitoring of hematological, blood chemistry, and immunologic parameters. The investigator must document all directly observed AEs and all spontaneously reported AEs. AEs will be documented on the AE eCRF in appropriate medical terminology. The severity and the relationship to the study intervention will be determined and reported on the eCRF.

Any intermittent or as needed use of any medication (specifically, any newly prescribed medication) during the course of the study may indicate the occurrence of an AE that may need to be recorded on both the AE eCRF and the concomitant medication form.

8.4.2 Serious Adverse Events

SAEs (whether or not they are also UPs) must be reported on the SAE/UP Report Form and sent to the Sponsor Clinical Safety Office (CSO) by fax or e-mail attachment. Deaths and immediately life threatening SAEs must be reported within 1 business day after the site becomes aware of the event. All other SAEs must be reported within 3 business days of site awareness.

SPONSOR CLINICAL SAFETY OFFICE CONTACT INFORMATION:

OCRPRO Clinical Safety Office
[name]
[name]

[contact]
[contact]
E-mail: [contact]

Non-US sites may have country specific SAE reporting requirements – refer to the MOPs for details.

8.4.3 Unanticipated Problems

Non-Serious AEs that are UPs must also be reported on the SAE/UP Report Form and sent to the CSO by fax or e-mail attachment no later than 7 calendar days of site awareness of the event. The UPs that are not AEs are not reported to the Sponsor CSO.

8.4.4 Pregnancy

Pregnancy itself is not an AE. However, complications of pregnancies are AEs and may be SAEs. Pertinent obstetrical information for all pregnancies will be reported to the CSO via fax or email within 3 business days from site awareness of the pregnancy.

Pregnancy outcome data (e.g., delivery outcome, spontaneous or elective termination of the pregnancy) will be reported to the CSO within 3 business days of the site's awareness on a protocol-specified form.

In the event of a pregnancy, the subject's treatment should be unblinded per the unblinding section of the protocol.

Pregnancy Outcomes should be reported to the Clinical Safety Office. However, if the Investigator learns at any time after a subject has completed the Day 28, End-of- Study visit, of an untoward medical occurrence that would have qualified as an SAE, and such event is reasonably related to previous study drug exposure, the Investigator should promptly notify the Sponsor and the IRB/IEC.

8.5 Investigator Reporting Responsibilities to the Site IRB/EC

8.5.1 Safety reports

Investigators are responsible for submitting Safety Reports and UP summaries that are received from the Sponsor to their local IRB/Ethics Committee. Investigators must also comply with all local IRB/Ethics Committee reporting requirements.

8.5.2 Expedited Reporting to the Site IRB/EC

Unanticipated problems that are either AEs or non-AEs, (as defined above) and protocol violations which do not meet the definition of a UP will be reported within 7 calendar days of investigator awareness (or as required by the site IRB/EC).

8.5.3 Annual Reporting to the IRB/EC

The following items will be reported to the IRB/EC in summary at the time of Continuing Review (or more frequently as required by the site IRB/ECs):

- All unanticipated problems
- All protocol deviations which in the opinion of the investigator should be reported
- Summaries of AEs recorded for this study

8.6 Follow-up of Adverse Events and Serious Adverse Events

AEs that occur following enrollment of the subject (by signing the informed consent) are followed until the final outcome is known or until the end of the study follow-up period (Study Day 28).

SAEs that have not resolved by the end of the follow-up period are followed until final outcome is known. If it is not possible to obtain a final outcome for an SAE (e.g., the subject is lost to

follow-up), the reason a final outcome could not be obtained will be recorded by the investigator on the AE CRF (if the CRF is still open) and the SAE/UP Report Form.

SAEs that occur after the study follow-up period that are reported to and are assessed by the Investigator to be possibly, probably, or definitely related must be reported to the CSO, as described above.

8.7 Safety Monitoring

8.7.1 Study Monitoring

The trial will be conducted in compliance with this protocol, International Conference on Harmonization (ICH) Guidelines for Good Clinical Practice (GCP) and any applicable regulatory requirement(s). This study monitoring will be conducted according to the “NIAID Intramural Clinical Monitoring Guidelines.” Monitors under contract to the NIAID will visit the clinical research site to monitor all aspects of the study in accordance with the appropriate regulations. The objectives of a monitoring visit will be:

1. To verify the prompt reporting of all data points, including reporting SAEs, and also check the availability of signed informed consent.
2. To compare individual subjects records and the source documents (supporting data, laboratory specimen records and medical records to include physician progress notes, nurse’ notes, subjects’ hospital charts).
3. To ensure compliance with the protocol, and accuracy and completeness of records.

The monitors also will inspect the clinical site regulatory files to ensure that regulatory requirements (national requirements, US FDA) are being followed. During the monitoring visits, the Investigator (and/or designee) and other study personnel will be available to discuss the study progress and monitoring visit.

The Investigator (and/or designee) will make study documents (e.g., consent forms and electronic case report forms (eCRFs)) and pertinent hospital or clinical records readily available for inspection by the local IRB/IEC, the local and national regulatory authorities, the US FDA, the site monitors, and the NIAID staff for confirmation of the study data.

